### **C. Motivational factors related to Exercise Maintenance: Reward Sensitivity and Self-Regulation**

The motivational aspect of our 3-month progressive exercise paradigm is based on both the Transtheoretical Model (TTM) of health behavior change and Self-Determination Theory (SDT) for exercise, which integrates well with the TTM stages of exercise behavior change and captures internal motivation to adopt and sustain exercise. Importantly, SDT is based on theories of self-regulation and learning. Thus, SDT supports our contention that capacities for *self-regulation and reward-based learning* will constitute neuropsychological manifestations of the effects of our 3-month training program on NPY system function and underlie motivation to sustain exercise. Our hypotheses are also supported by empirical evidence demonstrating that self-efficacy and intrinsic motivational factors predict TTM-defined active stages of behavioral change, including exercise maintenance, in the general population. This accords with recently published findings from our laboratory in a CP/PTSD population. Among trauma-exposed women with fibromyalgia (73% with PTSD), there was a large effect size for higher levels of self-efficacy in the action and maintenance stages of exercise, even in the context of higher fibromyalgia-related interference. The means and standard deviations for self-efficacy in the non-active, pre-contemplative/preparatory vs. active stages of change were  $38.64 \pm 7.15$  vs.  $51.4 \pm 9.45$ , respectively:  $F(1,16)=2.02$ ,  $p=.17$ ,  $n^2=.11$ . To our knowledge this is the first study to examine exercise-related self-efficacy and TTM stages of change for exercise in a trauma-exposed CP population. These findings support our current proposal and suggest that even with a high level of pain-related symptoms, patients with CP/PTSD who have or achieve a high degree of exercise self-efficacy will have an increased likelihood of sustaining exercise long-term.

Anhedonia, or loss of pleasure, is a transdiagnostic symptom of psychopathology observed in both depression and PTSD. Clinical neuroscience research into the mechanisms underlying anhedonia has drawn on a rich animal literature on the neural systems that support healthy reward processing. This experimental animal research has elucidated two psychologically and neurobiologically distinct systems that support reward processing. These include 1) *reward anticipation*, or interest in pursuing reward-relevant items or activities, which is mediated primarily by mesolimbic dopaminergic mechanisms; and 2) *reward consumption*, or the capacity for pleasure upon receiving a reward, which is supported by a neural network including prefrontal regions implicated in reward valuation, and 'hedonic hotspots' in the ventral striatum and brainstem. Clinical neuroscience research in humans suggests that both components are implicated in depression and PTSD. As such, the proposed project will examine exercise-training associated change in each of these components of reward sensitivity in relationship to changes NPY system function—as well as in relationship to change in symptoms of anhedonia, depression and PTSD, self-efficacy and intrinsic motivation to exercise, and exercise maintenance.

A recent meta-analysis found more pronounced executive function deficits in PTSD patients compared to trauma-exposed controls. In addition, male gender, older age, war trauma, and higher severity of co-morbid depressive symptoms were related to poorer executive functioning among the trauma-exposed. For our study, we will utilize the Go/No-Go task to investigate the relationship between executive function as a measure of self-regulation and NPY system function. Slowed central processing of No-Go stimuli and more rapid responding to Go stimuli in a Go/No-Go task have been related to PTSD hyperarousal and re-experiencing symptoms. PTSD patients also showed weaker activation of ventromedial (vm) PFC than trauma-exposed controls in the No-Go vs. Go condition; vmPFC activation, in turn, correlated negatively with fear-potentiated startle during safety signal learning and fear extinction. Deficits in frontal lobe activation during performance

of this task by patients with PTSD also predicted poorer outcome in response to cognitive behavioral therapy. Such studies thus support our hypothesis that baseline plasma NPY levels and release of NPY in response to exercise will correlate with response inhibition in this task—and that capacity for response inhibition will correlate with self efficacy, which in turn will contribute to the prediction of exercise maintenance.

Pain-related interference was clinically reduced between the baseline ( $M=4.4$ ,  $SD=1.2$ ) and endpoint ( $M=3.6$ ,  $SD=1.3$ ) ( $p=0.47$ ) assessments, yielding a Cohen's  $d$  of .6 (medium effect size). Resting NPY before exercise training was weakly correlated with pain-related interference ( $r= -.36$ ,  $p=.43$ ), while resting NPY after exercise training was more strongly correlated ( $r= -.67$ ,  $p=.15$ ). Consistent with [name] previous findings, peak NPY levels reached during CPX testing were positively correlated with pain threshold ( $r=.60$ ,  $p=.20$ ) after (but not before) exercise-training. In addition, the change between resting and peak NPY levels correlated strongly with pain threshold ( $r=.96$ ,  $p<.001$ ). Furthermore, the change in peak NPY reached during CPX testing after 3-months of exercise-training correlated with the change in pain tolerance ( $r=.64$ ,  $p=.12$ ).

Severity of depression measured by the Beck Depression Inventory (BDI-II) was reduced between the baseline ( $M=28.4$ ,  $SD=15.4$ ) and endpoint ( $M=17.0$ ,  $SD=15.5$ ) ( $p=0.05$ ), yielding a Cohen's  $d$  of .73 (medium to large effect size). Resting NPY before training was not correlated with depression severity ( $r=.05$ ,  $p=.91$ ), but resting NPY after exercise-training was inversely correlated ( $r= -.61$ ,  $p=.15$ ).

Preliminary data also demonstrate a strong correlation between changes in the capacity for NPY release during the CPX (measured as the change from resting to peak CPX levels) across exercise-training and improvements in SDT-based intrinsic motivation ( $r=.96$ ,  $p=0.008$ ) and self-efficacy ( $r=.99$ ,  $p=.014$ ) for exercise.

Thus our preliminary results from this small sample trend in the direction of our hypotheses with effect sizes in the medium to large range.

#### **E. Summary of Significance**

- (1) This study will establish whether exercise-induced changes in NPY system function are associated with changes in putative mechanisms that predict exercise maintenance—a problem that has dogged proponents of exercise as a health benefit for many years. If so, exercise programs can be calibrated to optimize/maintain changes in NPY system function, to more efficiently and effectively deliver immediate and long-term health benefits to patients with CP/PTSD and reduce health care costs.
- (2) This non-pharmacological approach also could be used as an adjunct to existing cognitive-behavioral PTSD or pain therapies to enhance their efficacy—and potentially reduce progression to opiate use with the attendant risks of abuse, dependence, morbidity and death.

#### **INNOVATION**

- (1) The proposed exercise paradigm represents a shift from general exercise prescriptions to a clinically feasible, rigorous individually tailored approach. Baseline CPX testing is used to inform the participant's exercise prescription based on heart rate range (HRR) rather than exercise type, thus controlling for exercise intensity. Data from our preliminary work and Pernow show that the threshold for NPY release during exercise is strongly correlated with the anaerobic threshold and occurs at a *mean* of 75% of  $VO_2$  max.

Progressively targeting individually determined HRRs to eventually reach the anaerobic threshold associated with NPY release will increase the likelihood that NPY synthesis and release will be upregulated across training. Using HRR as the exercise target also allows participants to choose their preferred exercise type (i.e. walking, running, cycling or swimming) and may increase the likelihood of long-term exercise maintenance. (2) Restoring or increasing the capacity to release NPY during stress through exercise is a novel PTSD and CP treatment approach, as well as a novel means to increase the likelihood of exercise maintenance via effects on capacities for reward and self-regulation.

(3) Integrating biological and neuropsychological constructs to improve therapies for the complex CP/PTSD population is novel and more likely to reduce disability and negative health consequences in the long-term.

## APPROACH

**Overall Strategy:** The proposed research will assess effects of a rigorous, individually tailored 3-month progressive exercise training in patients with CP/PTSD on NPY system function during a standardized cardiopulmonary exercise test (CPX) as related to changes in pain sensitivity, depression and PTSD, reward sensitivity and self-regulation, and TTM motivational constructs related to exercise maintenance.

**Participant Characteristics, Recruitment Strategies, Screening Evaluation:** See Human Subjects section.

**Scheduling of Women:** Each cold pressor and CPX session in women will be scheduled 2-6 days after the start of menses during the early follicular phase (when estrogen and progesterone levels are low and stable), or after initiation of a new pill cycle in women on oral contraceptives. Women on other types of steroid contraception will be scheduled as convenient as steroid levels are generally constant.

Measures	Eligibility Screening Session	Baseline Resting CPT	Baseline CPX/CPT	Midpoint Resting CPT	Post-Train Resting CPT	Post-Train CPX/CPT	F/UP 1 & 3 Month
Baseline Dx Status							
SCID-5, LEC-5, CAPS-5	X						
BAT-L	X						
Pain Ratings							
WHYMPI- Interference	X		X	X		X	X
Numerical Rating Scale	X	X	X	X	X	X	X
Cold Pressor Test		X	X	X	X	X	
Psychiatric Symptoms							
BDI-II, PCL-5/CAPS-5	X		X	X		X	X
CSSRS	X			X		X	
Exercise Behavior							
TTM Stage Change	X		X	X		X	X
Exercise Motivation							
TTM Self-Efficacy/ SDT EMS	X		X	X		X	X
Executive Function & Self-Regulation							
Go/No-Go Task			X			X	
Generalized Self-Efficacy			X	X		X	X
Emotion Regulation Scale			X	X		X	X
Reward Sensitivity							
TEPS & EEfRT			X	X		X	X
Blood Biomarkers	X	X	X	X	X	X	

1. *Structured Clinical Interview for DSM-5 (SCID)-5:* This current gold-standard clinician-administered interview will be used to diagnose psychiatric and substance abuse disorders except for PTSD (see below).

2. *Life Events Checklist (LEC-5):* The LEC-5 will be used to code exposure to potential traumatic experiences and serve as a reference for the CAPS-5 assessment.

3. *Clinician-Administered PTSD Scale-5 (CAPS-5):* This 30-item structured interview yields a dichotomous diagnosis of PTSD and a continuous score of severity for each symptom. The CAPS-5 is currently being validated, but the previous version CAPS-IV demonstrated excellent sensitivity (.81) and specificity (.95).

4. **VA Boston Assessment of Traumatic Brain Injury (BATL) Military and Civilian versions:** The BAT-L is the first validated semi-structured clinical interview to characterize head injuries due to blast or blunt neurotrauma and diagnose TBIs throughout the lifespan.

5. **Beck Depression Inventory (BDI-II):** The BDI is a well-validated 21-item self-report measure of depressive symptom severity. It yields a total score and subscale scores for depressive cognitive and somatic symptoms.

6. **PTSD Checklist (PCL-5):** The PCL is a 20-item self-report that assesses the extent to which an individual is bothered by each PTSD symptom during the past month using a 5-point Likert-type scale. The PCL-5 is undergoing validation, but the previous PCL based on DSM-IV had good sensitivity (.82) and specificity (.83).

7. **Columbia Suicide Severity Rating Scale (CSSRS):** This validated scale is used routinely in clinical trials to assess historical and current risk for self/other harm.

**Transtheoretical Model of Exercise Stage of Change:** This 23-item continuous measure categorizes stages of behavioral change (precontemplation, contemplation, preparation, action and maintenance).

8. **Self-Efficacy for Exercise:** This 18 item scale is used to determine confidence in one's ability to exercise.

9. **Exercise Motivation Scale:** This 31 item scale is used to determine extrinsic and intrinsic variants of exercise motivation based on Self-Determination Theory. Results from various analyses showed adequate evidence for the a priori hypothesized EMS factorial structure, acceptable subscale reliability estimates, and nomological validity.

10. **Go/No-Go Task:** This computerized task measures response inhibition. Participants are asked to respond to certain ("go") stimuli and make no response "no-go" stimuli, while maintaining speed and accuracy. The main dependent measure is the commission error rate (making a "go" response to "no-go" trials).

11. **Generalized Self-Efficacy Scale:** This revised 10-item scale taps into a global sense of self-efficacy, or belief by an individual in his or her ability (e.g., "I can always solve difficult problems if I try hard enough," and "I can usually handle whatever comes"). This 10-item self-report scale assesses habitual use of two common strategies to alter emotion captured on two sub-scales: cognitive reappraisal and expressive suppression. Items are rated on a 7-point Likert scale from 1 (strongly disagree) to 7 (strongly agree).

12. **Temporal Experience of Pleasure Scale (TEPS):** This 18-item self-report measure uses a Likert-like scale (1-6) to assess reward sensitivity. Two sub-scales with convergent and discriminant validity assess anticipatory and consummatory aspects of reward sensitivity.

13. **Effort Expenditure for Rewards Task (EEfRT):** This computerized (Matlab) task (for which scripts have been obtained from the developer for study use) captures willingness to expend effort for rewards. EEfRT scores have been inversely related to anhedonia. The task has been validated in healthy college students and adults with major depression and schizophrenia.

**Cardiopulmonary Exercise Test (CPX):** The symptom limited CPX test controls for confounders that potentially impact NPY. Participants will present to the VA Clinical Studies Unit (CSU) at 7:30 am after having fasted except for water after midnight. Urine toxicology and pregnancy testing, vital signs, and an EKG will be obtained, and a standardized 6 kcal/kg breakfast of carbohydrate/protein power bars will be provided. An IV then will be placed. The CPX is performed after two hours of rest and during which rating scales (see below) will be administered. The CPX test is performed per guidelines published by the American College of Cardiology. During the CPX (performed on an upright bicycle), EKG tracing and intermittent BP readings, functional capacity (oxygen consumption or peak VO2) and ventilatory anaerobic threshold (VAT) are measured to assess safety and fitness. Blood samples are obtained at -15 and 0 minutes before exercise and at each 3-minute increase in exercise load set by a standardized bike ramp protocol adjusted for age, bodyweight, and pre-test approximation of fitness. Rapid early adjustment of load based on the heart rate response (HRR) by the exercise physiologist allows all subjects to reach their maximum exercise load within comparable ~15 minute time frames. Achievement of peak VO2 max is based on meeting 2 of 3 criteria: 1) respiratory exchange ratio >1.1; 2) plateau of VO2 with increased load; 3) age-targeted heart rate achievement; 4) inability to continue pedaling. If, at any time, participants wish to terminate or are unable to perform the CPX, the session will be terminated after an appropriate and safe cool-down period. See Humans Subjects section for additional safety procedures employed to ensure participant safety.

**Cold Pressor Test (CPT):** Per standard CPT procedures, participants will hold their right hand, up to the wrist, in a temperature controlled ice water bath, while keeping the hand still. They are instructed to say when they first experience pain and to withdraw their hand when the pain becomes intolerable. Pain threshold is defined as the number of seconds between hand immersion and the first report of "pain." Pain tolerance is defined as the number of seconds between hand immersion and hand withdrawal from the water. To prevent risk to subjects, a 7-minute time limit for immersion, unknown to the patient, is imposed. The CPT is performed just before and 30' after CPX testing to assess effects of acute exercise on pain sensitivity. To assess effects of exercise training on resting pain sensitivity, the CPT also will be performed 1-

2 days before each CPX and at the exercise-training midpoint. At these sessions, participants will engage in the same procedures (except the CPX) at the same time of day as those performed at the CPX sessions.

**Progressive Exercise Training Program:** After the initial CPX and CPT sessions, participants return to the CSU for 2 exercise-training sessions with our exercise physiologist. A pre-programmed heart rate monitor that “beeps” when exercise intensity increases is provided to participants to ensure that the targeted HRR is reached in accordance with individualized progressive exercise prescriptions. After these sessions, the exercise physiologist will instruct participants to gradually increase the frequency of their prescribed exercise sessions at home (per protocol) to 3x/week by week 4. During weeks 4, 7, and 10 an investigator will call participants to check-in and discuss any barriers to exercise. Basic motivational interviewing techniques (i.e. reflective listening) and problem solving strategies (the current standard of care in this area) will be used to facilitate exercise compliance while maintaining safety. To verify home exercise, participants will wear an actigraph and heart rate monitor that measures activity and heart rate. Data from the heart rate monitor will be downloaded and reviewed with participants upon return to the clinic for test sessions.

**Exercise Prescription:** The exercise prescription entails a 10 minute warm-up and cool down at 30-50% HRR. The exercise portion lasts 30 minutes, initially at 40-60% HRR during weeks 1-2 followed by incremental increases in the HRR range by 10% every two weeks through week 6 (midpoint) when the exercise intensity is increased to 70-80% HRR and held there during weeks 7-12.

**Exercise Training Follow-Up:** Phone calls will be made at 1- and 3-months follow-up after completion of exercise training and testing. Ratings will be administered to determine whether exercise and improvements in symptoms and motivation have been sustained, as well as to identify barriers to continued exercise.

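### The plan names only commission errors as a Go/No-Go score, so an NPY association in that task cannot be told apart from a difference in response speed

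*Combined protocol and SAP*

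**What the plan says.** Measure 10 in the Approach section describes a computerised task in which participants respond to go stimuli and withhold to no-go stimuli "while maintaining speed and accuracy". It then says "The main dependent measure is the commission error rate". No other score from this task is named anywhere.

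Section C of Significance gives the purpose: "we will utilize the Go/No-Go task to investigate the relationship between executive function as a measure of self-regulation and NPY system function". It predicts that "baseline plasma NPY levels and release of NPY in response to exercise will correlate with response inhibition in this task". The same section reports from the literature that "more rapid responding to Go stimuli in a Go/No-Go task have been related to PTSD hyperarousal and re-experiencing symptoms"; the other subject of that sentence is slower central processing of No-Go stimuli.

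The measures table schedules the task twice, at the baseline and post-training CPX sessions. The Statistical Analysis Plan assigns Aims 1, 2 and 4 to unconditional latent growth models and Aim 3 to correlations followed by a discriminant function analysis. None of these has a term for Go reaction time or Go omissions.

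**The concern.** The commission rate uses no-go trials only. It falls when inhibition improves, but also when a person slows down or responds less often to everything; someone who never responds scores a perfect 0%. The instruction to keep up speed asks for the right behaviour, but nothing in the plan checks or uses the speed achieved.

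The protocol supplies a reason for speed to vary with NPY. Section C ties faster Go responding to PTSD symptoms. The Inclusion/Exclusion Criteria section cites literature linking PTSD severity to NPY deficits, and Hypothesis 4b expects PTSD symptoms to fall as NPY release rises. Following the signs: higher NPY goes with fewer symptoms, fewer symptoms with slower Go responses, and slower Go responses with fewer commission errors. That is the direction the study hopes to see, and it requires no link between NPY and inhibition.

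At stake is the interpretation of the one behavioural self-regulation task, on which section C rests its frontal-lobe argument.

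**Working it through.** **Inputs.** From the documents: n = 30, the commission rate as the named score, and two Go/No-Go sessions. The documents give no trial counts, error rates or reaction times, so every task parameter below is an assumption. The plan's only design figure is n = 30 for d = 0.5. The two-sided normal formula gives ((1.960 + 0.842)/0.5)² = 31.4, so 32, which is close to 30. It has no bearing on the Go/No-Go score; 30 is used here only as the sample size.

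**1. Ranking by commission rate against d'.** d' = z(hit rate) − z(commission rate), for three invented records:

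| Record | Go hits | Commission errors | d' |
|---|---|---|---|
| A | 99% | 20% | 2.33 + 0.84 = 3.17 |
| B | 85% | 10% | 1.04 + 1.28 = 2.32 |
| C | 50% | 2% | 0.00 + 2.05 = 2.05 |

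The commission rate ranks C best and A worst; d' reverses the order.

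**2. Responding less often, discrimination unchanged.** In an equal-variance signal-detection model with criterion c, commission rate = 1 − Φ(d'/2 + c) and omission rate = 1 − Φ(d'/2 − c). Take d' = 2.5 and move c from −0.5 to 0:
- commission: 1 − Φ(0.75) = 22.7% falls to 1 − Φ(1.25) = 10.6%;
- omission: 1 − Φ(1.75) = 4.0% rises to 1 − Φ(1.25) = 10.6%.

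The same shift takes commission errors from 30.9% to 15.9% at d' = 2.0, and from 15.9% to 6.7% at d' = 3.0.

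**3. Slowing, inhibition unchanged.** In a race model, P(commission) = Φ((inhibition time − Go RT)/√(80² + 50²)), with inhibition time 280 ms (SD 50), Go RT SD 80 and denominator 94.3:
- Go RT 380 ms: Φ(−100/94.3) = Φ(−1.06) = 14.5%;
- Go RT 410 ms: Φ(−130/94.3) = Φ(−1.38) = 8.4%.

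A 30 ms slowing alone removes about two fifths of the errors: (14.5 − 8.4)/14.5 = 42%.

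**4. Effect on the test at n = 30.** A correlation needs |r| ≥ 0.361 for two-sided p < 0.05. The race model was simulated with 4,000 replicates per setting, 50 no-go and 150 go trials, and between-person SDs of 40 ms (Go RT) and 25 ms (inhibition). The SD of speed change was 20 or 40 ms. Inhibition change had SD 0 or 20 ms and was independent of NPY. The adjusted test is the partial correlation given observed change in Go RT, (r_xy − r_xs·r_ys)/√((1 − r_xs²)(1 − r_ys²)), where x is NPY change, y is the reduction in commission errors and s is the change in Go RT.

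| Assumed NPY–speed correlation | Rejection, commission rate alone | Rejection, adjusted for Go RT change |
|---|---|---|
| 0.10–0.18 | about 5–11% | 4–6% |
| 0.3–0.5 | about 11–55% | 4–6% |

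At 0.3–0.5 the spurious correlation averages about 0.13 to 0.35.

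**5. Whether d' alone would do.** It depends on the mechanism. When people simply respond less often (step 2), a d' score rejects at about 5%. When they slow down but go hits stay stable, d' rises because commissions fall. With assumed hits of 98.5% and an NPY–speed correlation of 0.3–0.5, d' still rejects in about 8–41% of studies; with an assumed 600 ms response deadline, 6–14%. Go reaction time is therefore needed as well.

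**The case against.** A reader might infer that the commission rate is the only score the team will ever look at, or that response speed could generate the Aim 1 and Aim 3 results as a whole. The documents support neither. The text calls the commission rate the main measure, which leaves secondary scores unspecified rather than excluded. The measures table also lists the Generalized Self-Efficacy and Emotion Regulation scales under self-regulation. Both aims use reward measures (TEPS and EEfRT), and Aim 3 adds exercise self-efficacy and intrinsic motivation. None of these is scored from commission errors.

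The path from NPY to speed is also less firm than it may look. Hypothesis 4a predicts no baseline correlation between CPX-induced NPY and PTSD severity. The preliminary r of −.61 is for resting NPY after training, with p = .20. If PTSD were the only link, an assumed PTSD–speed correlation of 0.3 would give 0.61 × 0.3 = 0.18, at the low end of the range; reaching 0.5 would need 0.5/0.61 = 0.82. In addition, section C's sentence ties PTSD symptoms to altered No-Go processing as well as to Go speed, so a real inhibition effect is equally compatible with the protocol.

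Finally, Go reaction time after training may itself be part of what NPY changes, so adjustment could remove a genuine effect.

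All of this stands. It limits the scope and size of the point and argues against replacing the main score. It does not supply any means, within the plan, of separating inhibition from speed.

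**Conclusion.** The point holds for the Go/No-Go component of Aims 1 and 3 only. As scored and analysed, an NPY–commission association could reflect inhibition, response speed or both, and the plan has no analysis to tell them apart. The mechanism follows from the definition of the score and needs no data.

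Its size in this trial cannot be known. Under assumed NPY–speed correlations of 0.1 to 0.5, false positives at n = 30 run from about 5% (no inflation) to about 55%, against 4–6% after adjustment. The upper end requires a strong NPY–speed link that the documents do not establish. This is a worthwhile, inexpensive improvement to a mechanistic study, and no reason to discard the commission rate or to doubt the other self-regulation, reward or motivation findings.

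**What to change.** In measure 10 and in the Statistical Analysis Plan:

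- Keep the commission error rate as the main Go/No-Go score.
- Pre-specify that each NPY–Go/No-Go association is also reported adjusted for mean correct-Go reaction time at the same session, or for its change where the hypothesis concerns change.
- Name a companion score: Go omission rate, or d' from both trial types with a stated correction for rates of 0% and 100%. Do not rely on d' alone.
- For Aim 3, report Go reaction time and omissions beside the commission rate.
- State the reading rule in advance: describe an association as specific to inhibition only if the adjusted estimate is consistent with that; otherwise report it as not separable from response speed.

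**Cost.** Mostly wording. The same computerised task at the same two sessions should already record Go accuracy and reaction time, though the team should confirm that its output stores them. Adjustment uses one degree of freedom at n = 30 and may over-adjust if speed is part of the NPY effect, which is why both estimates are shown. One further step is needed: the planned growth models are unconditional and estimate a midpoint, but Go/No-Go has no midpoint assessment. The adjusted change analysis must therefore be written as a two-time-point model, such as a partial correlation or a regression of change.
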